5. STUDY DESIGN

This study is a single center, phase II randomized, double-blind, placebo-controlled clinical trial designed to assess the efficacy of intranasally (IN) administered glulisine versus placebo in patients with aMCI and probable mild AD.

After written informed consent has been obtained from the subject and family member/caregiver, subjects will be screened to assess study eligibility based on study inclusion/exclusion criteria. Subjects who are eligible at the end of the screening visit (Visit 1) will be scheduled for a baseline visit (visit 2). During the baseline visit, subjects will undergo neuropsychological testing with the ADAS-Cog 13 battery and supplemental tests including the Trailmaking Test Parts A & B, Digit Span, Controlled Oral Word Association Test, Animal Naming, and WMS logical memory to establish a baseline. Repeat cognitive assessments will be performed at 12 and 24 weeks. Patients will also be assessed on two additional measures for olfaction (Alberta smell test) and sleep measures (Sleep Questionnaire and ESS) at baseline, 12 weeks, and 24 weeks. Patients enrolled in the AD biomarker substudy will undergo a baseline FDG-PET scan and CSF biomarkers (Abeta42, tau, phosphotau) at baseline and 24 weeks.

A total of n=90 subjects will be randomized to receiving either IN glulisine (n=45) or placebo (n=45) two times daily (morning and evening, separate by at least 8 hours). In addition, subjects will be block randomized based on ApoE4 status, presence of non-insulin dependent diabetes, and MOCA score (18-22 vs. 23-27). Subjects will receive either 0.2 ml IN insulin (20 IU) (0.1ml/10 units IN in each nostril) or placebo administered two times daily over a 6 month period.

5.1. Outcome Measures

Neuropsychological, functional, and depression batteries will be performed at screen/baseline, Visit 7 and at Visit 10 (refer to section 7.4 for full description) to assess primary endpoint. A subset of subjects will undergo testing for CSF biomarkers (Abeta42, tau, phosphotau) and FDG-PET imaging at baseline and Visit 10 to address exploratory endpoints.

5.2. Study Duration

Study participation will last approximately 8 months, consisting of a minimum of 7 days but no more than 4 week screening phase and baseline visit, and a total of 9 treatment/safety visits over 6 months. If study visit window exceeds 28 days, study drug will be resupplied which may require additional study drug pickup visits. Patients who discontinue treatment will continue follow-up measures as possible and will be analyzed as randomized per the intent to treat principal.

6. STUDY POPULATION

6.1. Eligibility Criteria

6.1.1. Inclusion Criteria

A subject will be included for consideration in this study only if all of the following criteria are met:

1. Male or female subject with a clinical and research diagnosis of amnesic-mild cognitive impairment (1, 2) OR probable mild AD in accordance with NINCDS-ADRDA criteria (3).
2. Subject has a MOCA score of 18-27.
3. Subject has a Hachinski Ischemia Score ≤ 4 .
4. Subject is ≥ 50 and <90 years of age.
5. Female subjects must be at least 2 years post-menopausal or surgically sterile.
6. The subject must be proficient in speaking, reading and understanding English in order to comply with procedural testing of cognitive function, memory and physiology.
7. Subject has a dedicated family member/study partner, who will be able to attend all visits and report on subject's status.
8. Subject and family member/study partner have both provided fully informed written consent prior to participation. In the event that subject is legally unable to provide informed written consent due to deterioration in cognitive abilities, fully informed written consent must be provided by a legally authorized representative.
9. If AD, subject must have a brain CT or MRI in initial diagnostic workup or subsequent care that is compatible with the diagnosis of probable Alzheimer's disease.

6.1.2. Exclusion Criteria

A subject will *not* be included for consideration in this study if any of the following criteria are met:

1. Subject has medical history and/or clinically determined evidence of other CNS disorders including, but not limited to brain tumor, active subdural hematoma, seizure disorder, multiple sclerosis, dementia with Lewy bodies, vascular dementia, corticobasal syndrome, progressive supranuclear palsy, Parkinson's disease, multiple system atrophy, frontotemporal dementia, normal pressure hydrocephalus, Huntington's disease, or Jakob-Creutzfeldt disease presenting as dementia.
2. Subject has medical history and/or clinically determined disorders: current B12 deficiency, chronic sinusitis or any untreated thyroid disease, significant head trauma, or history of difficulty with smell and/or taste prior to AD diagnosis.
3. Subject has history of any of the following: moderate to severe pulmonary disease, poorly

controlled congestive heart failure, significant cardiovascular and/or cerebrovascular events within previous 6 months, condition known to affect absorption, distribution, metabolism, or excretion of drugs such as any hepatic, renal or gastrointestinal disease or any other clinically relevant abnormality that inclusion, would pose a safety risk to the subject as determined by investigator.

4. Subject has had previous nasal and/or oto-pharyngeal surgery and severe deviated septum and/or other anomalies.
5. Subject has history of any psychiatric illness, with the exception of major depressive and anxiety disorder (according to DSM-IV TR) currently in remission or stable with treatment for ≥ 2 years, or any other psychiatric condition that inclusion would pose a safety risk to the subject as determined by investigator.
6. Subject is currently taking any medications, herbals and food supplements that are medically/clinically contraindicated as determined by investigator in order to comply with procedural testing of cognitive function as well as ensure study safety. See list of prohibited medications and compounds.
7. Subject has undergone a recent change (≤ 1 month) in their prescribed acetylcholinesterase inhibitor (e.g. donepezil, rivastigmine, galantamine) or memantine.
8. Subject has undergone a recent change (< 1 month) in their SSRI or anti-depressant medication.
9. Subject has current or recent drug or alcohol abuse or dependence as defined by DSM-IV TR.
10. Screening laboratory results that are medically relevant, in which inclusion would pose a safety risk to the subject as determined by investigator.
11. The subject has participated in any other research study at least 3 months prior to
12. The subject has an insulin allergy.

1. Study assessments and procedures

A summary of study events and procedures is outlined in the Study Visit Table. Demographic, Screening, and Baseline Assessments are described in Sections 7.1.1-7.1.2, the Treatment Phase is outlined in Sections 7.1.3-7.1.10, and the Safety monitoring are detailed in Section 7.1.11; details of neuropsychological assessments are outlined in Section 7.4. Note that all visits are non-fasting unless otherwise noted.

7.1. Demographic and Baseline Assessments

7.1.1. Visit 1; Screening Visit Fasting

The following procedures will be performed at this visit:

- Obtain written informed consent from study partner and subject (or subject's legally authorized representative) prior to any study related procedures.
- Collect laboratory samples for screening assessment, for specific tests refer to Table 1.
- Administer MOCA.
- Obtain Hachinski Score.
- Administer Geriatric Depression Scale (GDS).
- Review Inclusion/Exclusion Criteria.

- Review medical history, as it pertains to inclusion/exclusion criteria, such as research diagnosis, disease severity, and course of AD.
- Obtain subject's demographic information (date of birth, gender, race, education, etc.).
- Obtain details of medications taken over the course of the last 30 days.
- Complete physical exam, including neurological exam. Collect vital signs, height and weight prior to ECG and blood draw.
- Perform a standard 12-lead ECG.

7.1.2. Visit 2; Baseline Visit

The following procedures will be performed at this visit:

- Review Inclusion/Exclusion Criteria.
- Collect vital signs and weight.
- Collect concomitant medication information and record AEs/SAEs.
- Neuropsychological testing with ADAS-Cog 13 and supplemental cognitive assessments.
- Administer CDR
- Administer Columbia-Suicide Severity Rating Scale (C-SSRS).
- Administer Functional Assessment Questionnaire (FAQ).
- Administer Alberta Smell Test.
- Administer sleep measures (Sleep questionnaire and ESS)
- Study Drug administration training.
- Hypoglycemia rescue training.
- Sub-study PET scan. For participating subjects, scan will be obtained within 1 week (\pm 3 days).
- Sub-study LP/ CSF. For participating subjects, procedure will be performed within 1 week (\pm 3 days).

7.1.3. Visit 3; Initial Treatment Visit; (Week 0)

The following procedures will be performed at this visit:

- Review Inclusion/Exclusion Criteria.
- Collect vital signs and weight.
- Collect concomitant medication information and record AEs/SAEs.
- Study Drug administration training.
- Study drug dispensing /diary.
- Administer study dose in clinic with subject/study partner.
- Obtain fingerstick blood glucose pre study dose and post study dose at 15 min, 30 min and 1 hour.
- Visit 4 scheduled within 1 week (\pm 3 days).

7.1.4. Visit 4; Follow-Up Safety Visit; (Week 1)

The following procedures will be performed at this visit:

- Collect concomitant medication information and record AEs/SAEs.
- Collect vital signs and weight
- Obtain laboratory studies.
- Administer study dose in clinic by subject/ study partner.
- Obtain fingerstick blood glucose pre study dose and post study dose at 15min, 30 min and 1 hour.
- Study drug administration training.
- Study drug dispensing/diary.
- Visit 5 scheduled within 3 weeks (\pm 3 days).

7.1.5. Visit 5; Treatment and Adherence; (Week 4)

The following procedures will be performed at this visit:

- Collect vital signs, and weight.
- Collect concomitant medication information and record AEs/SAEs.
- Review training of study drug administration.
- Study drug dispensing/diary.
- Visit 6 will be scheduled within 1 month (\pm 3 days).

7.1.6. Visit 6; Treatment and Adherence; (Week 8)

Following procedures will be performed at this visit.

- Collect vital signs and weight
- Collect concomitant medication information and record AEs/SAEs.
- Review training of study drug administration.
- Study drug dispensing /diary.
- Visit 7 scheduled within 1 month (\pm 7 days).

7.1.7. Visit 7; Treatment and Adherence; (Week 12)

Following procedures will be performed at this visit.

- Collect vital signs and weight.
- Collect concomitant medication information and record AEs/SAEs.
- Neuropsychological testing with ADAS-Cog 13 and supplemental cognitive assessments.
- Administer CDR.
- Administer FAQ.
- Administer GDS.
- Administer C-SSRS.
- Administer sleep measures (Sleep questionnaire and ESS)
- Administer Alberta smell test
- Review training of study drug administration.
- Study drug dispensing/diary.

- Visit 8 will be scheduled within 1 month (± 3 days).

7.1.8. Visit 8; Treatment and Adherence (Week 16)

Following procedures will be performed at this visit.

- Collect vital signs and weight.
- Collect concomitant medication information and record AEs/SAEs.
- Review training of study drug administration.
- Study drug dispensing/diary.
- Visit 9 will be scheduled within 1 month (± 3 days).

7.1.9. Visit 9; 5-month check-in (Week 20)

Following procedures will be performed at this visit.

- Collect vital signs and weight.
- Collect concomitant medication information and record AEs/SAEs.
- Review training of study drug administration.
- Study drug dispensing/diary.
- Visit 10 will be scheduled within 1 month (± 7 days).

7.1.10. Visit 10; 6 month follow-up (Week 24)

Following procedures will be performed at this visit.

- Collect vital signs and weight.
- Collect concomitant medication information and record AEs/SAEs.
- Neuropsychological testing with ADAS-Cog 13 and supplemental cognitive assessments.
- Administer CDR.
- Administer FAQ.
- Administer GDS.
- Administer Alberta smell test
- Administer sleep measures (Sleep questionnaire and ESS)
- Obtain repeat FDG-PET study in subgroup. Scan will be obtained within 1 week (± 3 days).
- Obtain repeat spinal fluid analysis in subgroup. Procedure will be performed within 1 week (± 3 days).
- Visit 11 scheduled within 1 month (± 7 days).

7.1.11. Visit 11; Final Safety and Discharge; Fasting (Week 28)

Following procedures will be performed at this visit.

- Collect vital signs and weight.
- Complete physical and neurological exam.

- Collect concomitant medication information and record AEs/SAEs.
- Collect laboratory samples, for specific tests refer to in Table 1.
- Perform a standard 12-lead ECG.
- Administer C-SSRS.

7.2. Early Withdrawal

If subject withdraws from the study after the screening visit, but before visit 3, no further evaluations are necessary. If subject withdraws from the study after visit 3, all safety assessments will be performed (see section 7.3).

7.3. Safety

For all safety assessments described below, any clinically significant change will be recorded as an AE or SAE.

7.3.1. Physical Examination

Complete physical examination will be performed at visits, 1 and 11, or if the subject withdraws or is withdrawn from the study early. Any abnormalities noted at Visit 1, will be documented as part of the subject's medical history.

7.3.2. Neurological Examination

Neurological examination will be performed at visits, 1 and 11, or if the subject withdraws early. Any abnormalities noted at Visit 1, will be documented as part of the subject's medical history.

7.3.3. Vital Signs

Vital signs will be recorded at all visits. For within subject consistency, brachial artery pressure will be obtained in the routine fashion, the same arm should be used for all study measurements.

Blood pressure and heart rate to be measured after subject has been sitting quietly for a minimum of 5 minutes. Diastolic blood pressure will be measured at the disappearance of Korotkoff sounds. Vitals sign will be monitored by clinical staff during each visit of the study.

In addition, vital signs will be measured pre and post study dose on Visits 3 and 4. The investigator will be notified for any baseline changes in blood pressure >20 mmHg systolic and >10 mmHg diastolic

A pre-dose fingerstick blood glucose will be measured followed by measurements post- study drug at 15 minute, 30 minute and 1 hour during visit 3 and 4. The investigator will be notified for any baseline changes. A blood glucose < 70 mg/dL will be considered clinically significant.

Vital signs will be taken prior to ECG and blood draw.

7.3.4. Weight

Body weight will be measured at all visits.

7.3.5. ECG

A standard 12-lead ECG will be performed on subjects at visit 1 and 11

7.3.6. Laboratory Samples

APOE genotyping procedure is discussed in Section 7.5.

All subjects will be required to fast for a minimum of 12 hours prior to collection of blood sampling on designated fasting visits.

7.3.6.1 HOMA-IR – Measure for Insulin Resistance

Calculation of HOMA-IR with Blood glucose and insulin level during Visit 1 using the following formula(45, 46);

$$\text{HOMA-IR} = [\text{glucose (nmol/L)} * \text{insulin } (\mu\text{U/mL})/22.5]$$

See **Table 1** for specific list of laboratory assessments.

Table 1 Laboratory Assessments

Procedure	Visit 1;	*Visit 3;	*Visit 4;	Visit 11;	Early Withdrawal
Basic Metabolic Panel (Na, K, CO ₂ , Cl, BUN, Creatinine, Glucose and Ca)	X		X	X	X
Insulin Level	X			X	X
CBC w/ Diff	X			X	X
Fingerstick Blood Glucose Baseline, post study dose, 15 min, 30 min and 1hour		X	X		
HbA1c	X				
APOE status	X				
Thyroid Stimulating Hormone (TSH)	X				
Vitamin B12	X				

***Blood samples to be collected after study dose is administered.**

7.4. Neuropsychological Assessment

See Table 2 for specific list of neuropsychological Assessment.

Table 2 Neuropsychological Assessment

Procedure	Screen	Baseline Phase	Treatment Phase		Follow-up	Early Withdrawal
	Visit 1	Visit 2	Visit 7	Visit 10	Visit 11	
FAQ		X	X	X		
GDS	X		X	X		X
ADAS-Cog 13		X	X	X		
CDR		X	X	X		
MOCA	X					
C-SSRS		X	X		X	X
Digit span forward/backward		X	X	X		
Trailmaking Parts A&B		X	X	X		
COWAT		X	X	X		
Animal naming		X	X	X		
WMS Logical Memory		X	X	X		
AST		X	X	X		
Sleep Questionnaire		X	X	X		
ESS		X	X	X		

7.4.1. ADAS-Cog 13 Summary

The ADAS-Cog was developed as an outcome measure for global cognition in clinical trials for Alzheimer’s disease. The ADAS-Cog assesses multiple cognitive domains including memory, language, praxis, and orientation (47). Overall, the ADAS-Cog has proven successful for its intended purpose with higher scores indicating greater cognitive impairment. The modified ADAS-Cog 13-item scale (48) includes all original ADAS-Cog items with the addition of a number cancellation task and a delayed free recall task, for a total of 85 points. The purpose of these additional items increases the number of cognitive domains and range of symptom severity to best assess subjects affected by the earlier stages of Alzheimer’s disease (e.g. amnesic MCI and mild AD).

7.4.2. Digit Span subtest from the Wechsler Adult Intelligence Scale -4th Edition (WAIS-IV)

The WAIS-IV Digit Span test is a brief measure of auditory attention, concentration, and working memory. Subjects are read a random list of numbers at a rate of one per second and immediately asked to repeat them in a forward sequence, a backward sequence, or to rearrange them in numeric order starting with the lowest number. Digit strings gradually expand and become lengthier until the subject makes consistent errors, at which point the test is discontinued. The test yields numerous scores for interpretation.

7.4.3. Controlled Oral Word Association Test (COWAT)

The COWAT is a short, paper/pencil measure of phonemic fluency and executive functioning from the Multilingual Aphasia Examination.

7.4.4. Trail Making Test, Parts A & B

The Trail Making Test is a brief paper and pencil measure of attention, processing speed, and mental flexibility (or set-shifting). The test has been well validated for use with a wide range of subject populations, is easy to administer, and has been shown to be sensitive in detecting subtle changes in central nervous system compromise and specifically changes in frontal lobe or “executive” functions. Part A requires subjects to connect a series of numbered dots in order as quickly as possible. Part B requires subjects to connect numbered and lettered dots as quickly as possible by alternating back and forth between the two without making mistakes. Scores include both time to completion and various error types.

7.4.5. Montreal Cognitive Assessment (MOCA)

The Montreal Cognitive Assessment (MoCA) was designed as a rapid screening instrument for mild cognitive dysfunction. It assesses different cognitive domains: attention and concentration, executive functions, memory, language, visuoconstructional skills, conceptual thinking, calculations, and orientation. The time to administer the MoCA is approximately 10 minutes. The total possible score is 30 points, and scores of 26 or above are considered normal.

7.4.6. Clinical Dementia Rating (CDR) Scale

The CDR is a 5-point scale used to characterize six domains of cognitive and functional performance applicable to Alzheimer disease and related dementias: Memory, Orientation, Judgment & Problem Solving, Community Affairs, Home & Hobbies, and Personal Care <http://alzheimer.wustl.edu/cdr/aboutcdr.htm>. The necessary information to make each rating is obtained through a semi-structured interview of the patient and a reliable informant or collateral source (e.g., family member).

The CDR table (http://knightadrc.wustl.edu/cdr/PDFs/CDR_Table.pdf) provides descriptive anchors that guide the clinician in making appropriate ratings based on interview data and clinical judgment. In addition to ratings for each domain, an overall CDR score may be calculated through the use of an [algorithm](#). This score is useful for characterizing and tracking a patient's level of impairment/dementia:

CDR-0.5 = very mild dementia

CDR-1 = mild

CDR-2 = moderate

CDR-3 = severe

In addition, the total CDR ratings for each of the six cognitive/functional domains can be added to create a CDR sum of boxes (SOB).

7.4.7. Columbia-Suicide Severity Rating Scale (C-SSRS)

The Columbia–Suicide Severity Rating Scale (C-SSRS) was designed to quantify the severity of suicidal ideation and behavior (49). In this study, suicidal ideation and behavior will be prospectively assessed using the C-SSRS. The C-SSRS will be administered by trained raters at specified time points, as indicated in the Visit Flow Chart, as well as at unscheduled visits as clinically indicated. Any subjects demonstrating evidence of suicidality will prompt immediate consultation with the site’s on-call psychiatrist for assistance with decision-making and potential referral to behavioral health services.

7.4.8. 15-Item Geriatric Depression Scale (GDS)

The 15-item GDS, a paper, interview-based depression screening tool will be administered to the subject and score by a qualified, trained rater.

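### The C-SSRS is not scheduled at Visit 10 (week 24), so weeks 12 to 24 of dosing have no scheduled on-treatment suicidality interview for subjects who complete the trial

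*Combined protocol and SAP*

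**What the plan says.** Section 7.4.7 sets the aim: "In this study, suicidal ideation and behavior will be prospectively assessed using the C-SSRS". It ties the interview to scheduled time points, allows it at unscheduled visits where there is clinical reason, and says that evidence of suicidality leads to prompt psychiatric consultation.

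The schedule appears in two places, which agree for Visits 1 to 11:

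- **Visit lists.** The C-SSRS is listed in 7.1.2 (Visit 2, baseline), 7.1.7 (Visit 7, week 12) and 7.1.11 (Visit 11, week 28: "Administer C-SSRS"). It is not in 7.1.8, 7.1.9 or 7.1.10 (weeks 16, 20 and 24). The Visit 10 list does include the depression scale ("Administer GDS") and the full cognitive and functional battery.
- **Table 2 in Section 7.4.** The C-SSRS row is marked at Visits 2, 7 and 11 and at early withdrawal. It is blank at Visit 10.

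The introduction to the study assessments assigns Sections 7.1.3 to 7.1.10 to the treatment phase, and Table 2 labels Visit 11 as follow-up. Exclusion criterion 5 in Section 6.1.2 rules out psychiatric illness "with the exception of major depressive and anxiety disorder (according to DSM-IV TR) currently in remission or stable with treatment", where stability must have lasted at least 2 years. Mood is a secondary objective (Section 3.2).

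**The concern.** Visit 10 is the natural end-of-treatment assessment, and the C-SSRS is the only repeated instrument left out of it. No reason is given. Suicidality that arises in the second half of dosing is first covered by a scheduled structured interview after treatment appears to have stopped. The consultation step in Section 7.4.7 therefore has no scheduled prompt from the C-SSRS at the end of treatment.

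The two mood-related instruments are also separated. A subject whose depression score has worsened at Visit 10 has no scheduled C-SSRS that day, and the C-SSRS at Visit 11 has no depression scale beside it. At scheduled visits after baseline, the two coincide only at Visit 7.

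What is at stake is how promptly and completely safety information is captured. Section 4.2 does not list suicidality as a safety endpoint and Section 12.3 plans no analysis of it, so the statistical operating characteristics are not involved.

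**Working it through.** The plan states no figure to reproduce; the check is schedule arithmetic.

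**Inputs**

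- Visit 7 = week 12, Visit 10 = week 24, Visit 11 = week 28 (headings of 7.1.7, 7.1.10 and 7.1.11).
- Visit windows: Visit 7 to 8, ±3 days (7.1.7); Visit 8 to 9, ±3 days (7.1.8); Visit 9 to 10, ±7 days (7.1.9); Visit 10 to 11, ±7 days (7.1.10). One month is taken as 28 days, as the week labels imply.
- Dosing runs for 6 months from week 0 (Sections 5 and 7.1.3). The last listed dispensing is at Visit 9, week 20 (7.1.9). End of dosing at about week 24 is inferred from these two facts.

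**1. Is the omission real, or a table-reading artefact?** The Visit 10 procedure list and the Table 2 row omit it independently, so it is real. The other repeated instruments in Table 2 (FAQ, GDS, ADAS-Cog 13, CDR, Digit Span, Trailmaking, COWAT, Animal Naming, WMS Logical Memory, AST, Sleep Questionnaire, ESS) are all marked at Visit 10. MOCA is given at screening only.

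**2. Interval between the last two scheduled interviews**

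- Nominal: 28 − 12 = 16 weeks = 112 days.
- Windows: 3 + 3 + 7 + 7 = 20 days, giving 112 − 20 = 92 to 112 + 20 = 132 days, or 13.1 to 18.9 weeks.

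**3. Lag from the inferred end of dosing to the next interview**

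- Nominal: 28 − 24 = 4 weeks.
- With ±7 days: 3 to 5 weeks.

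**4. Share of treatment after the only on-treatment interview**

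- (24 − 12) / 24 = 12/24 = 50%.

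**5. Effect of adding Visit 10**

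- Visit 7 to Visit 10: 24 − 12 = 12 weeks. Visit 10 to Visit 11: 4 weeks.
- The longest scheduled gap after week 12 falls from 16 to 12 weeks, and scheduled interviews between the start and end of dosing rise from one to two.

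**6. Early withdrawal.** Table 2 marks a C-SSRS at early withdrawal. Sections 7.2 and 10.2 call for the assessments in Section 7.3, which covers examinations, vital signs, weight, ECG and laboratory samples but not the C-SSRS. These passages do not agree, so early withdrawal cannot simply be counted as covered.

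**The case against.** The strongest reply is that nothing is contradicted. Section 7.4.7 promises assessment at specified time points; baseline, week 12 and week 28 are specified, and no document sets a minimum frequency. That stands: this is a design choice that can be improved, not a breach of the plan's own text.

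It is also fair that the second half of dosing is not unobserved. Adverse events are recorded at Visits 8, 9 and 10, the depression scale is given at Visit 10, a study partner attends all visits and reports on the subject's status, and an unscheduled C-SSRS is possible. The consultation step responds to any evidence of suicidality, not only to a scheduled interview. These safeguards narrow the gap. None is a scheduled suicidality interview, and the unscheduled route needs someone to suspect a problem first.

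Two stronger readings are tempting but not supported:

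- **That the week 28 interview relies on 16-week recall by memory-impaired subjects.** The documents give neither the C-SSRS version nor its recall period. If the question covers the time since the last interview, events from weeks 12 to 24 would be about 4 to 16 weeks old at week 28, but that is an inference. The study partner may also contribute information.
- **That the trial admits a broadly depressed population.** The 2-year stability condition, the exclusion of other psychiatric illness and the exclusion of recent antidepressant changes (criterion 8) all limit this.

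**Conclusion.** The point holds as a modest safety-monitoring gap that is cheap to close. For completers, the only scheduled C-SSRS between the start and end of dosing is at week 12. The next is 16 weeks later (13.1 to 18.9 with windows) and about 4 weeks (3 to 5) after dosing appears to end. Half of the treatment period follows the only on-treatment interview.

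This rests on two assumptions. End of dosing at week 24 is inferred; if dosing continued past Visit 10 the 4-week lag would shrink, but the 16-week interval would not change. The Visit Flow Chart to which Section 7.4.7 refers is not in the text available for review, so its agreement with Table 2 could not be checked.

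A reader might infer that suicidality goes unmonitored in weeks 12 to 24. The documents do not support that, because the partial safeguards listed above operate throughout. No efficacy estimate, power or error rate is affected.

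**What to change.** Add the C-SSRS to the Visit 10 list in Section 7.1.10 and mark it in the Visit 10 column of Table 2. Keep Visit 11 as the off-treatment assessment, and check that the Visit Flow Chart matches. If the omission is deliberate, state the reason.

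Reconcile Table 2 with Sections 7.2 and 10.2 so that they agree on whether the C-SSRS is part of the early-withdrawal assessments.

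The cost is one short interview at an existing visit where a trained rater already gives the depression scale. The downside is a few more minutes at a long visit. The Visit 10 addition changes a measurement schedule only; no dose, treatment rule or planned analysis changes.
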